1. Based on the results of gut microbiome sequencing, ELISA (antiphospholipid antibodies), and biochemical blood analysis in the main and control groups, we determine the dynamic changes of those parameters during COVID-19 rehabilitation.
2. According to the results, the effectiveness of Saumal itself regarding these 2 parameters will be evaluated.
3. Develop recommendations and an algorithm for patient management after COVID-19 to prevent complications.

Study Design

Study Type: Interventional

Primary Purpose: Treatment

Interventional Study Model: Parallel Assignment

Number of Arms: 2

Masking: None (Open Label)

Allocation: Randomized

Enrollment: **60 patients.** Originally, we planned to include 38 patients in the main group and 37 in the control group. Overall, these groups were evenly divided, with 30 patients in each group.

Arms and Interventions

Arms	Assigned Interventions
Experimental: Main Group Patients who had suffered from COVID-19 in the six months before the start of the study. Patients will receive Saumal (freeze-dried mare milk) for four weeks.	Dietary Supplement: Freeze-dried Mare Milk (Saumal) Freeze-dried Mare Milk (Saumal) is frequently reported for having therapeutic and dietary properties associated with specific chemical composition and certain physical properties of the product. It contains a total of about 40 biologically active components, the most important of them vitamins A, C, B1, B2, B6, and B12, amino acids, enzymes, and trace elements (low molecular weight peptides, lactalbumins, and globulins). Saumal will be administered to patients at a dose of 25 grams of dry powder per 200 ml of water, 2 times a day, 30 minutes before the meal, for 4 weeks.
No Intervention: Control Group Patients who had suffered from COVID-19 in the six months before the start of the study. There will be no intervention.	

Eligibility

Minimum Age: 18 Years

Maximum Age: 75 Years

Sex: All

Gender Based: No

Accepts Healthy Volunteers: No

Inclusion Criteria:

Age 18 years and older;

Patients in rehabilitation after COVID-19;

Signed informed consent;

Presence of patient's history of COVID-19, reliably established by PCR+ /presence of IgG/ diagnosis of coronavirus pneumonia on Computer Tomography based on discharge from hospital or outpatient records.

Exclusion Criteria:

Chronic inflammatory bowel disease;
Gut microbiota transplantation;
Chronic pancreatic disease, period of exacerbation;
Liver cirrhosis, Metavir stage 3-4;

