Any disease in the decompensation stage;
Neuralgic and psychological disorders that interfere with the study;
Cancer;
Non-transportable patients;
Patients who do not reside in Almaty;
Patients who have refused to participate in the study.

Examined for eligibility - 76 people;

Confirmed eligible - 60 people. According to our strict exclusion criteria, we had to remove 16 people [8 – oncological patients, 5 – moved house, 3 patients refused to participate];

Included in the study - 60 patients;

Completing follow-up and analysed - 60 patients.

Statistical Analysis Plan

Gut microbiota:

IBM SPSS ver. 23.0 (Chicago, IL, USA) was used to determine the statistical significance of the obtained data. All the indicators were verified for compliance with the law on normal distribution. If the variables obeyed this law, the Student's paired t-test was applied to determine statistical significance between the values before and after milk intake. Otherwise, the Wilcoxon sign rank criterion was used.

A single-factor analysis of variance was employed to verify the effect of administering freeze-dried mare's milk, which could potentially affect the indicators of gut microbiota.

Antiphospholipid antibodies:

The 95% confidence interval for aPL value was calculated for both median and mean. The confidence interval for the latter one was calculated in the descriptive statistics menu in IBM SPSS ver. 23.0 (Chicago, IL, USA).

It is necessary to find the value of the confidence coefficient (Student's criterion (t)) in the table of critical t-values, considering the total number of respondents (n) to find out a confidence interval for the median with a given confidence probability (p). After that, the calculation of the natural integer number (C) is needed for such a probability value: $C_p = (n/2 - t(p) \sqrt{n}/2)$. The lower confidence limit for the median is $X (C_p)$, where X is the ordinal number of the value in the ranked variation series corresponding to the lower boundary of the confidence interval. The upper confidence limit for the median is $X (n + 1 - C_p)$, where X is the ordinal number of the value in

the ranked variation series corresponding to the upper boundary of the confidence interval.

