If the normal distribution law is followed, the Student's paired t-test was used to determine statistical significance between values before and after freeze-dried mare's milk. If not, the Wilcoxon sign rank criterion was used for intergroup comparison. One-way analysis of variance (ANOVA) was used to determine the relationship between the mare's milk prescription factor and aPL levels in both groups.

Quality of life:

IBM SPSS ver. 23.0 (Chicago, IL, USA) was used to determine the statistical significance of the obtained data. All the indicators were verified for compliance with the law on normal distribution. If the variables obeyed this law, the Student's paired t-test was applied to determine statistical significance between the values before and after milk intake. Otherwise, the Wilcoxon sign rank criterion was used.

A single-factor analysis of variance was employed to verify the effect of administering freeze-dried mare's milk, which could potentially affect the quality-of-life scores.

Results section

Gut microbiota analysis.

In the main group, after taking freeze-dried mare's milk, there was a decrease in the content of bacteria phyla Bacteroidetes, Proteobacteria, Verrucomicrobia and Chloroflexi (by 3.03%, 2.83%, 0.47% and 0.16, respectively), and an increase in the content of bacteria phyla Nitrospirae, Tenericutes, Cyanobacteria, Spirochaetes, Euryarchaeota, Actinobacteria and Firmicutes (by 0.02 %, 0.05%, 0.15%, 0.17%, 0.24%, 1.42% and 7.62%, respectively).

The Fusobacteria phylum was absent according to the results of mare's milk intake in all respondents. The Elusimicrobia phylum, on the contrary, was present in some respondents as a result of therapy.

Attention is also drawn to the presence of the Synergistetes phylum, which was absent in the control group both before and after therapy. Moreover, the difference between the Firmicutes, Proteobacteria, Chloroflexi, Cyanobacteria and Synergistetes phyla was statistically significant (Table 1).

Table 1. The percentage terms of all phyla of the gut microbiota in the main group before and after taking freeze-dried mare's milk (CI - confidence interval).

Phylum name	Before	After	95% CI (t-student)	p (t-student)
Bacteroidetes	32,32%	29,43%	-0,01; 0,07	0,178
Firmicutes	45,31%	51,87%	-0,09; -0,02	0,001
Proteobacteria	9,25%	6,52%	0,1; 0,28	<0,001
Actinobacteria	3,75%	4,9%	-0,15; 0,14	0,951
Euryarchaeota	1,28%	1,52%	-0,42; 0,1	0,204
Verrucomicrobia	1,29%	0,83%	-0,09; 0,32	0,223

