The proportion of Bacteroidetes and Firmicutes in the gut microbiota is most significant. Summarizing their values in the main and control groups, we can see that their content increased in the former and decreased in the latter. Statistical analysis revealed a significant difference in the content of these phyla between the main group compared to the control group (Table 3).

Table 3. The percentage terms of Bacteroidetes and Firmicutes phylum in the main and control groups.

Main group			Control group		
Bacteroidete s+Firmicutes (before)	Bacteroidetes +Firmicutes (after)	p (Wilcoxon)	Bacteroidete s+Firmicutes (first test)	Bacteroidetes +Firmicutes (second test)	p (Wilcoxon)
77,63%	81,3%	0,026	78,76%	75,87%	0,213

To determine the effect of freeze-dried mare's milk on the gut microbiota at the phylum level, a one-factor analysis of variance was performed. A statistically significant relationship between such a factor as the administration of freeze-dried mare's milk was revealed in the Firmicutes, Elusimicrobia and Proteobacteria phyla (Table 4).

Table 4. The relationship between the use of prescribed freeze-dried mare's milk and indicators of gut microbiota at the phylum level.

Phylum name	p (One-way ANOVA)
Bacteroidetes	0,180
Firmicutes	0,048
Proteobacteria	0,043
Actinobacteria	0,186
Euryaychaeota	0,403
Verrucomicrobia	0,583
Chloroflexi	0,220
Cyanobacteria	0,280
Spirochaetes	0,340
Nitrospirae	0,143
Tenericutes	0,657
Fusobacteria	0,140
Elusimicrobia	0,044
Bacteroidetes + Firmicutes	0,037

Overall, the intake of freeze-dried mare's milk by post-COVID patients primarily contributed to an increase in the content of the sum of two major phyla of gut microbiota — Bacteroides and Firmicutes, with the latter being particularly significant. There is also a notable decrease in the number of bacteria from the Proteobacteria phylum in the main group, which includes representatives of pathogenic microflora.

Antiphospholipid antibody analysis.

29 out of 30 main group patients (96.67%) had normal IgM and IgG levels before taking freeze-dried mare's milk. In the case of the control group, aPL levels were normal in all respondents. The aPL levels were normal in patients of both groups after the second ELISA (Table 5).

Table 5. Antiphospholipid antibody scores of each patient in the main and control groups after two assays (aPL -antiphospholipid antibodies).

Main group		Control group					
aPL (before)		aPL (after)		aPL (first assay)		aPL (second assay)	

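### Table 4 is limited, without explanation, to phyla detected in both arms, so the highlighted Synergistetes finding rests on a within-arm test only

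*Combined protocol and SAP*

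**What the plan says.** The Statistical Analysis Plan, under Gut microbiota, has two layers: a paired test of before against after, and a test of the milk effect. The second is described thus: "A single-factor analysis of variance was employed to verify the effect of administering freeze-dried mare's milk, which could potentially affect the indicators of gut microbiota". No list of phyla, no detection rule and no multiplicity rule accompanies it.

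In the Results section, Gut microbiota analysis, Table 1 is captioned "The percentage terms of all phyla of the gut microbiota in the main group before and after taking freeze-dried mare's milk" and Table 2 is the control counterpart, also said to cover all phyla. The text above Table 1 says: "Attention is also drawn to the presence of the Synergistetes phylum, which was absent in the control group both before and after therapy". It then states that "the difference between the Firmicutes, Proteobacteria, Chloroflexi, Cyanobacteria and Synergistetes phyla was statistically significant (Table 1".

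The test of the milk effect is reported in "Table 4. The relationship between the use of prescribed freeze-dried mare's milk and indicators of gut microbiota at the phylum level". That table has no row for Synergistetes, Caldithrix or Thermotogae. It does have a row for the sum of Bacteroidetes and Firmicutes, which the SAP does not name.

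**The concern.** A randomised comparison answers whether milk changed a phylum by comparing the arms. A significant paired change in one arm does not do that, and these data show why. Of the five phyla called significant in Table 1, Chloroflexi (0.011) and Cyanobacteria (0.028) have between-arm p-values of 0.220 and 0.280 in Table 4. The discrepancy also runs the other way: Elusimicrobia is 0.109 in Table 1 and 0.044 in Table 4. Synergistetes is the only one of the five for which the reader cannot make this check.

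The contrast drawn with controls needs care as well. Table 1 shows the phylum in the milk arm before any milk was taken, so the arms already differed in its presence at baseline. A reader who takes the highlighted sentence together with the significance sentence may credit that difference to milk.

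Finally, detection in both arms is an observed property of the samples. As a filter for the between-arm table it should have been stated in advance, or at least reported.

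**Working it through.** **Which rows are missing**

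| Set | Number of phyla |
|---|---|
| Table 1 (milk arm) | 14 |
| Table 2 (control arm) | 15 |
| In either table | 16 |
| In both tables | 13 |
| Table 4, excluding the sum row | 13 |

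The 13 phyla in Table 4 are exactly the 13 common to Tables 1 and 2. The three left out are those listed in one arm only: Synergistetes (milk) and Caldithrix and Thermotogae (control).

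Zero means did not prevent testing elsewhere. Elusimicrobia is in Table 4 with printed means of 0.00% in the milk arm before and in the control arm at the second test. Fusobacteria (0.00% after milk) and Nitrospirae (0.00% at the second control test) are there too.

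**Reproducing the printed p-value**

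Inputs: Table 1, Synergistetes, 0.01% before and 0.09% after, 95% CI -0.14 to -0.02, p = 0.009; group size from Study Design, Enrollment ("with 30 patients in each group").

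- Mean change = (-0.14 - 0.02)/2 = -0.08, which matches 0.01 - 0.09.
- SE = half-width / t(0.975, 29 df) = 0.06/2.045 = 0.0293.
- t = -0.08/0.0293 = -2.73 on 29 df, p = 0.0107.
- Rounding of the two limits allows p from 0.006 to 0.018, so the printed 0.009 is compatible.

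**The missing between-arm test, approximated**

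Assumptions: the ANOVA is run on change, and control change is exactly zero with zero variance because the phylum was absent at both control tests.

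- SD of change in the milk arm = 0.0293 × √30 = 0.161.
- Pooled variance = (29 × 0.161² + 29 × 0)/58 = 0.161²/2.
- SE of the difference = √(0.161²/2 × 2/30) = 0.0293.
- t = 0.08/0.0293 = 2.73 on 58 df (F = t² on 1 and 58 df), p = 0.0084.
- Range from rounding of the limits: 0.004 to 0.015. Starting from the printed p = 0.009 (t = 2.80), p = 0.007.

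The 58 degrees of freedom rest on an equal-variance assumption that fails by construction when one arm is constant. Welch's test on change has 29 df here and returns the paired result itself: 0.0107 from the rounded limits, or the printed 0.009.

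**Multiplicity, taking two-sided 0.05 as the level (none is stated)**

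- Table 4 as printed: 14 unadjusted tests; family-wise error if independent = 1 - 0.95^14 = 0.51.
- Bonferroni threshold for 16 phyla = 0.05/16 = 0.0031.
- The low end of the Synergistetes range (0.004) is above this. Bonferroni-adjusted, 0.0084 × 16 = 0.13.
- The smallest p now in Table 4 is 0.037 (the sum row), against 0.05/14 = 0.0036 for the table as it stands.

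**The case against.** A reader might infer that the between-arm table was chosen on its results. The documents do not support that. They state no selection rule, and the visible pattern is mechanical: a phylum is in Table 4 if both arms list it. The two control-only phyla left out had non-significant changes (0.160 and 0.454), clearly non-significant phyla were kept, and the omitted Synergistetes test would probably have been the smallest unadjusted p in the table. Leaving it out did not favour the product.

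A reader might also infer that the text claims a significant difference between arms for Synergistetes. It does not. The highlighted sentence is descriptive, the significance sentence openly cites the milk-arm table, the ANOVA sentence names only Firmicutes, Elusimicrobia and Proteobacteria, and the closing summary of the microbiota results does not mention Synergistetes. The baseline facts are also on the page: the control absence is given for both times, and Table 1 prints 0.01% before milk.

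It can further be said that the SAP lists no phyla, so no stated list is breached; that leaving a phylum with one constant arm out of an ordinary ANOVA is defensible; and that with controls at zero a Welch test adds nothing numerically to the paired p.

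Most of this stands, and it limits the point to reporting and interpretation. It does not remove the point. The restriction is unexplained, the SAP gives no basis for it, the baseline difference has to be pieced together from a sentence and a table cell, and the highlighted result has neither a between-arm row nor a multiplicity adjustment.

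**Conclusion.** The point holds in a limited form. Table 4 leaves out 3 of 16 phyla without explanation, and one of them is a phylum that the text highlights against controls and lists as significant on a within-arm test alone. Its presence in one arm only was already there before milk.

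The illustrative between-arm result is nominally below 0.05 (about 0.008, range 0.004 to 0.015; 0.009 to 0.011 with Welch) but does not survive Bonferroni correction for 16 phyla. It should therefore be reported and not presumed positive. These p-values assume analysis of change, 30 patients per arm and exact zeros in controls. The documents do not say whether Table 4 analyses change or post-treatment values; in the latter case the p-value cannot be recovered from what is printed. The size of 0.08 percentage points further assumes that the interval is on the raw percentage scale. That fits this row but not every row of Table 1: for Proteobacteria the interval midpoint is 0.19, against a printed difference of 2.73.

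This is worth correcting because it is cheap and bears on a highlighted statement. It does not alter the stated conclusion on the gut microbiota.

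**What to change.** 1. Report the between-arm comparison for all 16 phyla, and say whether it is made on change or on post-treatment values.
2. For Synergistetes, Caldithrix and Thermotogae, where one arm is at zero, use a test that does not assume equal variances: Welch on change, or a rank or permutation test.
3. Show multiplicity-adjusted p-values across the table beside the unadjusted ones.
4. State that the Synergistetes presence/absence difference between arms existed at baseline.
5. Base the Synergistetes sentence on the adjusted between-arm result, or label it a descriptive within-arm observation.

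The cost is three more rows from data already held, one extra column and one reworded sentence. The downside for the sponsor is less favourable p-values: under Bonferroni none of the between-arm results now called significant in Table 4 (0.037 to 0.048) would remain so. That is already true of the 14 tests as printed and is not caused by the added rows.

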After bringing the variables to the normal distribution, the statistical significance was found in the control group only (Table 8).

Table 8. Statistical analysis of normally distributed antiphospholipid antibody levels.

	95% CI	p-value (t-student)
Main group, IgM	-0,03; 0,11	0,185
Main group, IgG	-0,07; 0,11	0,726
Control group, IgM	0,04; 0,14	0,001
Control group, IgG	0,05; 0,15	0,0001

ANOVA was performed to determine the direct effect of the natural food product on the aPL values (Table 9). ANOVA did not reveal any statistical significances.

Table 9. Finding the effect of the freeze-dried mare's milk on the antiphospholipid antibody values (ANOVA - analysis of variance).

Antibody name	p (One-way ANOVA)
IgM	0,541
IgG	0,938

aPL values in almost all patients of both groups were ranged normally. The intersection of all confidence intervals of medians and means indicates the absence of statistical significance between these indicators. The results before and after bringing the aPL values to normal distribution differ greatly, especially for the IgM level in the main group. One-factor analysis of variance also showed the lack of significance of the studied factor. These several theses can explain the given results. First, initial aPL values could have been normalized over 6-9 months after COVID-19. Second, there were screening kits in the study. Therefore, the obtained results do not show the levels of specific phospholipids (phosphatidylcholine, phosphatidylethanolamine, aCL, anti- β 2-GP1, etc.). Third, the severity of COVID-19 was not considered as an inclusion criterion.

Quality of life analysis.

The quality of life of post-COVID patients in the main group statistically significantly improved in both physical and mental health components after using mare's milk. In the control group, there was no statistically significant change in quality-of-life indicators for both physical and mental health components. Even though the average score for the physical component in the control group is higher than in the main group, the level of statistical significance and the confidence interval of both groups allow us to conclude that freeze-dried mare's milk can have a positive effect on this indicator of the quality of life of post-COVID patients (Table 10).

Table 10. The average quality-of-life score in patients of the main and control groups.

	Quality-of-life components							
	Physical				Mental			

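### Five rows of Tables 1 and 2, including the significant Cyanobacteria row, print a confidence interval and p-value that cannot come from one paired t-test on 30 pairs

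*Combined protocol and SAP*

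**What the plan says.** Under Enrollment, the document says that "these groups were evenly divided, with 30 patients in each group". The participant flow at the end of the eligibility section adds "Completing follow-up and analysed - 60 patients". No loss to follow-up and no missing stool or blood sample is reported in the text available.

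For gut microbiota, the Statistical Analysis Plan says that for normally distributed variables the "Student's paired t-test was applied to determine statistical significance between the values before and after milk intake", with the Wilcoxon signed-rank test otherwise. It describes no transformation, no handling of zero abundances and no exclusion of patients.

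Tables 1 and 2 carry one interval column and one p-value column per phylum, both labelled Student t, with no number of pairs. From Table 1 the text concludes: "Moreover, the difference between the Firmicutes, Proteobacteria, Chloroflexi, Cyanobacteria and Synergistetes phyla was statistically significant". For Cyanobacteria the table prints 0.16% before, 0.31% after, interval -1.95 to -0.17, p = 0.028.

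Table 8 gives similar pairs of figures for the antiphospholipid antibodies, after a transformation towards normality whose type is not given in the text available.

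**The concern.** A paired t-test yields its 95% interval and its p-value from the same mean, standard error and degrees of freedom. Once the number of pairs is known, one determines the other up to rounding. If the two disagree at 30 pairs, either the test did not use 30 pairs, or one of the printed figures is wrong or comes from another procedure.

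This matters most for Cyanobacteria, which is among the five phyla declared significant in the main group. A reader takes that as a result in 30 patients. If it describes about six, that is a fifth of the arm, and the reader cannot tell which fifth or how it was chosen. The other four failing rows carry no significance claim, but they are offered as whole-group results and their intervals or p-values cannot be relied on.

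**Working it through.** **Inputs.** n = 30 per group (Enrollment; participant flow). Interval limits and p-values from Tables 1, 2 and 8. Two-sided test assumed.

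**Formula.** For limits L and U, centre c = (L + U)/2 and half-width h = (U − L)/2. Then t = |c|/h × t(0.975; n − 1) and p = 2 × P(T > t) on n − 1 degrees of freedom. At n = 30 the multiplier is 2.045. Limits were varied by ±0.005 (rounding) and again by ±0.01 (to cover truncation), and p by ±0.0005.

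**A row that reproduces.** Main-group Chloroflexi, 0.04 to 0.28: c = 0.16, h = 0.12, t = 0.16/0.12 × 2.045 = 2.727, p = 0.0107; printed 0.011. Main-group Firmicutes, Proteobacteria and Synergistetes are also compatible with 30 pairs. Of the 33 rows in the three tables, 25 are.

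**Main-group Cyanobacteria.** c = −1.06, h = 0.89.
- n = 30: t = 1.06/0.89 × 2.045 = 2.436, p = 0.0212 (rounding 0.0206 to 0.0219; ±0.01 gives 0.0199 to 0.0226). Printed 0.028.
- n = 5: 0.0297. n = 6: 0.0281. n = 7: 0.0268. Under rounding only n = 6 fits; with ±0.01, n = 5 to 8.

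**All five failing rows:**

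| Row | Interval | p implied at n = 30 | Range, rounding | Range, ±0.01 | Printed p | n that fits (rounding) |
|---|---|---|---|---|---|---|
| Table 1 Cyanobacteria | −1.95; −0.17 | 0.021 | 0.0206–0.0219 | 0.0199–0.0226 | 0.028 | 6 |
| Table 1 Tenericutes | −0.20; 0.01 | 0.075 | 0.061–0.090 | 0.050–0.109 | 0.491 | none |
| Table 2 Euryarchaeota | −0.74; 0.24 | 0.305 | 0.296–0.315 | 0.287–0.325 | 0.209 | 4 |
| Table 2 Verrucomicrobia | −0.97; 0.85 | 0.894 | 0.885–0.902 | 0.876–0.911 | 0.871 | 5–8 |
| Table 2 Cyanobacteria | −1.42; 1.89 | 0.774 | 0.769–0.778 | 0.764–0.783 | 0.728 | 6 |

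**Tenericutes.** An upper limit of 0.1 instead of 0.01 gives p = 0.50 at n = 30 (rounding 0.459 to 0.544), which covers 0.491. The centre becomes −0.05, which is the printed change (0.04% to 0.09%). A one-digit slip explains this row; a small n does not.

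**Weaker rows.**
- Main-group Verrucomicrobia (printed 0.223): 0.241 to 0.281 under rounding, 0.222 to 0.304 at ±0.01.
- Main-group IgM in Table 8 (printed 0.185): 0.199 to 0.315 under rounding, 0.155 to 0.388 at ±0.01.
- Main-group Euryarchaeota (printed 0.204): 0.2045 to 0.2326 under rounding, which meets the printed value at its edge. Not counted.

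**Scale.** The Cyanobacteria centre of −1.06 does not match the printed change of 0.16 − 0.31 = −0.15 percentage points, nor −0.0015 as a proportion. Chloroflexi's centre of 0.16 does match its change (0.23 − 0.07 = 0.16 points), while Bacteroidetes, centred at 0.03 against 0.3232 − 0.2943 = 0.029, looks like a proportion. Scales therefore appear mixed within one table, without a label.

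**The case against.** **The tolerance may be too strict.** This stands for main-group Verrucomicrobia and main-group IgM, which fit 30 pairs if the limits were truncated. For IgM, the pages just before Table 8 were not available to this review and could state a number of pairs. A reader might count eight failing rows; the tables support five. Control Verrucomicrobia is the narrowest of these (0.876 at the edge against 0.871) and would fit at ±0.01 if its interval were a 99% one, which the label contradicts. Cyanobacteria reaches 0.028 at 30 pairs only by combining ±0.01 with a normal-quantile interval and a t-based p-value, which is not paired t-test output.

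**Zero abundances.** A reader might infer that a log transformation dropped every patient with a zero, so that Cyanobacteria was tested only in patients selected by outcome. The off-scale centres make this possible, but the document does not say it, and it was not done throughout. Fusobacteria was absent in all main-group patients after treatment, yet its row fits 30 pairs (0.201 to 0.261 against 0.247). Main-group Elusimicrobia, 0.00% before, fits as well (0.081 to 0.109 against 0.109). A p-value taken from a different test would be another explanation.

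**Consequence.** A reader might infer that Cyanobacteria loses its significance. It does not on these figures: the interval excludes zero, and p is 0.028 at n = 6 and 0.021 at n = 30. Nor does the document claim a between-group effect there; Table 4 gives p = 0.280. The closing paragraph of the gut microbiota results relies on Firmicutes, Bacteroidetes + Firmicutes and Proteobacteria, none of which is a failing row. This objection stands, and it limits the point to inconsistent reporting.

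**Conclusion.** The point holds for five rows: main-group Cyanobacteria and Tenericutes, and control Euryarchaeota, Verrucomicrobia and Cyanobacteria. Their intervals and p-values contradict the stated 30 pairs per group. Tenericutes is probably a misprint. The other four agree with about four to eight pairs, and one of these, main-group Cyanobacteria, is declared significant on figures that fit about 6 of 30 patients. Main-group Verrucomicrobia and IgM need a recheck only.

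This rests on taking the column labels at face value (95% intervals and two-sided p-values from the same paired t-test) and on all 30 patients per group contributing a pair. Whether the cause is an undisclosed subset, an undisclosed transformation or a wrong figure cannot be settled from the document.

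**What to change.** - Recompute the five rows from the existing data on all 30 pairs per group, and correct the interval or the p-value, including the Tenericutes upper limit. Recheck main-group Verrucomicrobia and main-group IgM at the same time.
- Print, for every row of Tables 1, 2 and 8, the number of pairs and the scale or transformation used.
- Where the differences are not normal, use the plan's own Wilcoxon signed-rank fallback on untransformed values of all patients, without excluding those with a zero at one visit. The standard signed-rank test sets aside pairs with no change, including zero at both visits, so state how many there are and how they are handled.
- Keep Cyanobacteria in the list of significant phyla only if it holds in that analysis. Otherwise withdraw it, or state the subset that it describes.

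The cost is a small rerun on data already in hand and the possible loss of the within-group Cyanobacteria claim.
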